9. ATTACHMENTS

1. PERIOD ALLOCATION OF ADVERSE EVENTS

Solicited events will always be allocated to the Post-dose 1 or Post-dose 2 period, as appropriate.

Unsolicited AEs will be allocated to the different periods per the following rules:

Step 1: Allocation of unsolicited events to the periods/phases:

The AEs present in the database are allocated to periods/phases based on their start date/time. If the start date/time of an event falls between (or on) the start and stop date/time of a period/phase, the AE is attributed to that period/phase (ie, AEs following vaccination).

Incomplete dates (ie, time and/or day and/or month and/or year missing):

- 1) In case of partial start or stop dates, the events are allocated to the periods/phases using the available partial information on start and end date; no imputation will be done. If, for instance, for the AE start date only month and year are available, these data are compared to the month and year information of the periods/phases. This rule may lead to multiplication of the event because of its assignment to multiple periods/phases (see below example).
- 2) In case of a completely missing start date, the event will be allocated to the appropriate period/phase (eg, Post-dose 1 or Post-dose 2) and consequently the Regimen period; except if the end date of the AE falls before the start of the Post-dose 1 or Post-dose 2 period.
- 3) In case of a completely missing end date (ie, only for the calculation of duration):
 - In case the AE is flagged as ongoing the date is imputed by the cut-off date of the analysis for subjects still ongoing in the study, and by the end date of the last period/phase for subjects who discontinued or completed the trial.
 - In case the AE is not flagged as ongoing, the end date is considered as unknown, and the date will remain missing.

Examples:

Screening Phase: start date: 14JUN2016 - stop date: 28JUN2016
Post-dose 1 period: start date: 28JUN2016 - stop date: 19JUL2016

1) Adverse event: start date: JUN2016- stop date: 15JUL2016

As the start date only has information about month and year, only this information will be used from the periods/phases (ie, assuming any day of Jun is possible) and therefore the AE will be assigned to the Screening Phase as well as to the Post-dose 1 period.

2) Adverse event: start date: JUL2016- stop date 14JUL2016

As the AE starts after the Screening Phase and after the start of the Post-dose 1 period, it is only assigned to the Post-dose 1 period.

Remarks:

- In addition to the date information, time information is considered to allocate AEs to periods, if available.

- The imputation of missing end dates of ongoing AEs will only be used to derive the duration of the event (ie, to give an indication of the minimum duration). The imputed end dates will not be shown in the data listings.

Step 2: Combination of events:

Overlapping/consecutive events are defined as events of the same subject with the same preferred term which have at least 1 day overlap or for which the start date of an event is 1 day after the end date of the preceding event. Overlapping/consecutive events may be combined into one AE or not, according to the following rules:

- 1) If overlapping/consecutive events start in a non-active phase (Screening or any of Post-dose FU phases) followed by an AE in an active (Post-dose 1 or Post-dose 2) period, they are allocated to their respective periods/phases and are considered as separate events.
 - 2) In case overlapping/consecutive events start within a single period/phase, they are considered as one and the same AE. The individual events which contribute to this AE are retained as individual records in the Analysis Data Model (ADaM) database but are assigned the same onset, period/phase, and total duration.
 - 3) In case overlapping/consecutive events start in an active period followed by a non-active phase, they are allocated only to the active period and are considered as one and the same AE. The individual events which contribute to this AE are retained as individual records in the ADaM database but are assigned the same onset, period, and total duration.
 - 4) In case an active period is followed by another active period, and the overlapping/consecutive events start in both periods, they are allocated to their respective period and are considered as separate AEs. The same rule applies for 2 non-active phases.
- Remarks:
 1. Time is not considered when determining overlap of events.
 2. Events can only be combined into one and the same AE if their start and stop dates are known.
 3. In case the completely missing end date is imputed (for calculation of duration), this date is also considered as a complete date.

Examples:

Screening phase: start date: 14JUN2016 - stop date: 28JUN2016

Post-dose 1 period: start date: 28JUN2016 - stop date: 26JUL2016

Post-dose 1 FU phase: start date: 27JUL2016 - stop date: 15AUG2016

Example for the above Scenario 1

AE1: start date: 20JUN2016- stop date: 10JUL2016

AE2: start date: 08JUL2016- stop date: 18JUL2016

AE1 will be attributed to the Screening Phase and AE2 to the Post-dose 1 period.

Example for the above Scenario 3

AE1: start date: 18JUL2016- stop date: 28JUL2016

AE2: start date: 28JUL2016- stop date: 08AUG2016

As AE1 starts in the active period (Post-dose 1) and overlaps with AE2 which starts in a non-active phase (Post-dose 1 FU), this AE is considered as a single AE in the AE analysis starting on 18JUL2016 and ending on 08AUG2016 and is attributed to the Post-dose 1 period.

2. TRANSFORMING ON-SITE ASSESSMENTS AND DIARIES OF SOLICITED ADVERSE EVENTS INTO AN ANALYSIS FORMAT

When creating the analysis dataset for solicited AEs, solicited AEs (recorded by day) need to be converted into the format of unsolicited AEs (recorded by event). All diary data will be considered, as well as any post-dose on-site assessment (scheduled as well as unscheduled) within (including the day of vaccination) 8 days after vaccination. For solicited local AEs for which a diameter is measured, the maximum of diameter derived grade and functional severity grading (if available) will be used. The start date of the AE will be considered as the date of first occurrence of the solicited AE (both local and systemic). If on subsequent day(s), the same grade is reported, the last reported date is used as the end date of the AE. A new record is created in case the grade of the event changes. If there is a time gap of at least one day between two (or more) occurrences of the same type of the solicited AE, then the second (and/or next) occurrence will be considered as a new AE. In case no data is reported for a day, this is analyzed as no event reported. If the on-site assessment differs in grade or relatedness (if collected) with the corresponding diary data, only the highest grade and relatedness assessment indicating the highest relatedness to study vaccination per AE will be kept in the analysis database and used in the tables and listings. The following example shows how the solicited AE should be converted into a format of unsolicited AEs:

Data from the Subject Diary

Subject: 0001

Solicited systemic AE: Headache

	On-site Assessment	Diary Data							
Solicited AE	Day 1 01Jan16	Day 1 01Jan16	Day 2 02Jan16	Day 3 03Jan16	Day 4 04Jan16	Day 5 05Jan16	Day 6 06Jan16	Day 7 07Jan16	Day 8 08Jan16
Grade	2	1	1	0	3	3	1	0	0
Relatedness	Doubtful	Probable							

The data should be converted and stored in the AE dataset as follows:

Subject No.	AE	Start Date (Char)	Stop Date (Char)	Severity	Relatedness	AEID
0001	Headache	01Jan16	02Jan16	2	Probable	1
0001	Headache	04Jan16	05Jan16	3	Probable	1
0001	Headache	06Jan16	06Jan16	1	Probable	1

If a solicited AE ends after Day 8:

The stop date of the event is the “Date of last day of symptom” as recorded in the eCRF and the “maximum severity” after Day 8 as recorded in the CRF. A separate record is created for this, in case this severity deviates from the previous record.

Note: To complete the start and end-date based on diary data, the date will be calculated based on the day the AE is reported relative to vaccination and not on the reported date. For example, if the vaccination is on 01-JAN-2016, and the AE starts on Day 3, the start date will be set to the 03-JAN-2016, independent of the reported actual date.

For the calculation of duration, the first and last day is used, irrespective of whether interruptions occurred in between by missing reporting days or Grade 0 events. In the above example, the 4 records contribute to the same AE, therefore AEID is set to the same value and the duration of the AE is set to 6 for all records.

It is important to note that the occurrence of solicited systemic adverse events considered to be related to the study vaccine and persisting for at least 3 days and in at least 3 subjects will result in a study pause. However, the above rule for calculating duration of AEs may incorrectly indicate that the pausing rule is met. Therefore, a listing of subjects with Grade 3 (severe) AEs will be generated with an indication that interruption between AE start and AE end are not considered in the calculation of the duration of the AEs.

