Day 380 (365 days Post-dose 2)	[336; 396]	≥ 274	366
Day 394 (365 days Post-dose 2)			

^a The analysis based on the per protocol (PP) analysis set will be restricted to data points that fall within this window (ie, protocol-defined window).

^b The analysis based on the immunogenicity analysis set will be restricted to data points that fall within this window.

Note 1: The analysis windows and target days are based on the relative day (ie, with respect to reference day [day of dose 1 or dose 2 administration]).

Note 2: Day of dose 2 is also considered as Day 1 with respect to the second vaccination (ie, for calculating target days that fall after the second vaccination).

Note 3: Day 36, Day 57, Day 195 and Day 380 apply only to the 14-day interval vaccination schedule. While Day 50, Day 71, Day 209 and Day 394 apply only to the 28-day interval vaccination schedule.

Table 3: Analysis Periods

Phase	Period	Interval	
		From	To
Screening		00:00 on the date of signing the informed consent form	One minute prior to dose 1 administration on Day 1
Regimen*	Post-dose 1	Date and time of dose 1 administration	Minimum of: 
 a) 23:59 on the date of last contact (for early study discontinuation) b) 23:59 on the date of relative Day 29 Post-dose 1 c) 23:59 on planned visit day of dose 2 administration (in case dose 2 is not administered) d) one minute prior to dose 2 administration [□] e) 23:59 on the date of database cut-off (in case of interim analysis)
Post-dose 1 FU		One minute after the end of the Post-dose 1 period	Minimum of: 
 a) 23:59 on the date of last contact (for early study discontinuation or completion) b) one minute prior to dose 2 administration c) 23:59 on the date of database cut-off (in case of interim analysis)
Regimen*	Post-dose 2	Date and time of dose 2 administration	Minimum of: 
 a) 23:59 on the date of last contact (for early study discontinuation or completion) b) 23:59 on the date of relative Day 29 Post-dose 2 c) 23:59 on the date of database cut-off (in case of interim analysis) 
Note: subjects who do not receive dose 2 will not have a Post-dose 2 period.

Post-dose 2 FU		One minute after the end of the Post-dose 2 period	Minimum of: 
 a) 23:59 on the date of database cut-off (in case of interim analysis) b) 23:59 on the date of last contact (for early study discontinuation or completion)

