7.1.3. Analysis Methods

In general, the AEs following vaccination will be summarized (ie, tables of descriptive statistics) by vaccination schedule and presented per period/phase. Similar summary tables will also be provided pooled by vaccine (dose).

Furthermore, unsolicited AEs will be summarized (showing number and percentage) by System Organ Class (SOC) and Preferred Term (PT). Solicited AEs (recorded by day) will be converted into the analysis format of unsolicited AEs (recorded by event), as detailed in Attachment 2. These solicited AEs will be summarized by class (local, systemic) and Preferred Term. For

solicited as well as unsolicited AEs, tables focusing on severity will be created. Focus will also be on the relationship (to the study vaccine) of the solicited systemic and unsolicited AEs.

The SAEs, AEs with fatal outcome, AEs leading to permanent stop of study vaccination, Grade 3 AEs and IREs will also be listed. A table summarizing all those parameters will further be created and presented per analysis period and vaccination schedule. Summary tabulations by SOC and PT for each of the category of events (ie, SAEs, AEs with fatal outcome, AEs leading to permanent stop of study vaccination, Grade 3 AEs and immediate reportable events) will also be generated on the entire reporting period. Subject narratives will be generated for these events, except Grade 3 AEs.

For the most frequent (at least 10% of subjects in any vaccination schedule) solicited local and systemic AEs, the duration and time to first onset of the events will also be summarized. If a subject experiences more than 1 occurrence of a solicited event, the maximum duration of the events will be used. The time to first onset is defined as:

$$[\textit{date of first onset} - \textit{reference date} + 1]$$

The reference date is the start date of each vaccination period (ie, Post-dose 1 or Post-dose 2). Duration and time to onset of AEs will be expressed in days.

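### An unsolicited AE dated to the dose 2 day without a start time is counted in both Post-dose 1 and Post-dose 2 when dose 2 is given by relative Day 29

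*SAP*

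**What the plan says.** SAP Attachment 1, Step 1 allocates unsolicited AEs to periods by start date and time. Its rule for partial dates covers a missing time as well as a missing day, month or year: "Incomplete dates (ie, time and/or day and/or month and/or year missing". For such dates, "the events are allocated to the periods/phases using the available partial information on start and end date; no imputation will be done". The SAP accepts the consequence: "This rule may lead to multiplication of the event because of its assignment to multiple periods/phases". A later remark adds that "time information is considered to allocate AEs to periods, if available".

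SAP Table 3 (Section 2.1) closes Post-dose 1 at the earliest of several limits. Two matter here: "23:59 on the date of relative Day 29 Post-dose 1" and "one minute prior to dose 2 administration". Post-dose 2 opens at the date and time of dose 2. If dose 2 comes after relative Day 29, a Post-dose 1 follow-up phase fills the gap.

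SAP Section 7.1.3 presents AEs by vaccination schedule and by period, and adds: "Similar summary tables will also be provided pooled by vaccine (dose". An overview of SAEs, fatal AEs, AEs that permanently stop vaccination, Grade 3 AEs and IREs is also shown per period. The SOC/PT tables for those categories cover the entire reporting period.

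Solicited AEs are outside Step 1. Attachment 1 fixes each of them to Post-dose 1 or Post-dose 2.

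**The concern.** The per-period and by-vaccine tables exist to show what follows each injection, and the two schedules give the same two vaccines in opposite order. If dose 2 is given by relative Day 29, the dose 2 calendar day belongs to two active periods. An unsolicited AE dated to that day without a clock time then appears under both doses, and hence under both MVA-BN-Filo and Ad26.ZEBOV. The same applies to an untimed SAE, Grade 3 AE or IRE in the per-period overview.

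The SAP's worked examples of multiple assignment concern month-only dates, where the day really is unknown. Here the day is known and only the order relative to the injection is open. The plan gives no tie-break for that case.

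The dose 2 day is a full clinic visit, so AEs dated to it are plausible. Protocol Section 7 requires the time of each injection to be recorded. I found no corresponding requirement for the start time of an AE.

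**Working it through.** **1. The SAP's own examples.** Attachment 1 has Screening from 14 to 28 June 2016 and Post-dose 1 from 28 June to 19 July 2016. Matching at the precision of the available date puts an AE starting in June 2016 in both Screening and Post-dose 1, and one starting in July 2016 in Post-dose 1 only. Both agree with the SAP. In this example, too, the two periods share a calendar date (28 June).

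**2. Dose 2 days to test.** Protocol Table 2 allows ±3 days: 15 ± 3 gives Days 12-18, and 29 ± 3 gives Days 26-32. Protocol Section 6.2 allows postponement up to 10 days beyond the window: 18 + 10 = Day 28 and 32 + 10 = Day 42.

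**3. Allocation.** The end of Post-dose 1 is the earlier of 23:59 on relative Day 29 and one minute before dose 2. Post-dose 2 starts at dose 2. For an unsolicited AE dated to the dose 2 day:

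| Dose 2 given on | No start time | Timed 2 hours after dose 2 |
|---|---|---|
| Days 12-18 | Post-dose 1 and Post-dose 2 | Post-dose 2 |
| Day 28 (postponed, 14-day schedule) | Post-dose 1 and Post-dose 2 | Post-dose 2 |
| Days 26-29 | Post-dose 1 and Post-dose 2 | Post-dose 2 |
| Days 30-32 | Post-dose 1 follow-up and Post-dose 2 | Post-dose 2 |
| Day 42 (postponed, 28-day schedule) | Post-dose 1 follow-up and Post-dose 2 | Post-dose 2 |

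**4. Does anything later remove the copy?** No. The remark on clock time works only when a time exists. Step 2, rule 4 keeps events in two consecutive active periods as separate AEs.

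**5. Which copy is spurious?** That depends on the event. Under the Time and Events Schedule notes and protocol Section 9.1.3, blood sampling, examination and vital signs on that day come before the injection. For a finding from one of these, the Post-dose 1 count is right and the Post-dose 2 copy is wrong. For an event that began after the injection, it is the other way round.

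**6. Size per affected subject.** The percentage moves only if the subject has no other counted AE in the wrongly credited period (for a preferred-term row, no other AE with that term). The increase is then 100/n points. With the planned cell sizes in SAP Table 1:

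- n=20 (Part 1 HIV-infected, active): 100/20 = 5.0
- n=40 (Part 1 healthy; each Part 2 Group 2 cohort, active): 100/40 = 2.5
- n=160 (each Part 2 Group 1 cohort, active): 100/160 = 0.625, about 0.6
- n=10 and n=5 (smaller placebo cells): 10 and 20

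For the healthy 14-day cohort pooled over Parts 1 and 2, n = 40 + 40 = 80, and the increase is 1.25.

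**7. What does not move.** The Regimen period combines both doses and a subject counts once in it, so its subject percentages are unchanged.

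**The case against.** The best defence is that the rule is disclosed and over-inclusive by design: it avoids imputation and loses no event from either period. It applies equally to placebo, no formal hypothesis test depends on it, and serious events and IREs are also listed and described in narratives. All of this is true and limits the consequences. It does not justify counting an event under two vaccines when its calendar day is known. Applying one rule to both arms does not cancel the effect either, because arms with more dose-day events gain more duplicates.

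A second objection concerns direction. A reader might infer that dose 2 reactions inflate the dose 1 vaccine's AE percentage. The documents do not support that as a general statement. The expected reactions (injection-site events, fever, headache and so on) are solicited and fixed to one dose. Clinically relevant laboratory, vital-sign and examination findings are recorded as AEs and come from assessments made before the injection. In the first-in-human study summarised in protocol Section 1.1, decreased neutrophils were the most frequent unsolicited AE. For findings of that kind the error falls on Post-dose 2. This objection stands, and it also rules out a fix that sends every untimed dose-day AE to Post-dose 2.

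Third, no overall inflation can be calculated. The documents give neither the frequency of missing AE times nor the eCRF layout. This stands too.

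**Conclusion.** The double count follows from the SAP text: every untimed unsolicited AE dated to the dose 2 day is assigned to both Post-dose 1 and Post-dose 2 when dose 2 is given by relative Day 29. That covers the whole 14-day-schedule window and Days 26-29 of the 28-day schedule. On Days 30-32 the duplicate goes to the follow-up phase, so Post-dose 1 is not affected.

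One of the two copies is always wrong, but which one depends on whether onset came before or after the injection. No one-directional bias can be claimed. The total size is unknown; only the effect per affected subject can be given, and it is large in the small cells. The result assumes that Step 1 is programmed literally and that some AE start times are missing.

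The Table 3 footnote on the dose 2 limit refers to dose 2 given before the Day 29 visit. If that limit does not apply on Day 29 itself, Post-dose 1 would run to 23:59 that day and overlap Post-dose 2 even for timed events. The result for untimed events is the same under either reading.

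**What to change.** Add to Attachment 1, Step 1: when only the start time is missing and the start date equals a vaccination date, allocate the AE to one period.

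- Use the preceding period or phase if the AE derives from a pre-injection assessment that day (laboratory sample, vital signs, physical examination) or if the CRF shows onset before the injection.
- Otherwise use the period that starts with that vaccination.

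Apply the same rule to Screening versus Post-dose 1 on Day 1. Keep multi-period assignment only for dates missing the day, month or year, and flag the affected events in the listing.

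The SAP already resolves a similar case: for safety baselines (SAP Section 2), an assessment on the dose 1 date counts as baseline when its time is missing.

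The cost is one SAP sentence, one programming condition and a way to identify AEs that come from pre-injection assessments. The remaining downside is small: an untimed AE that began before the injection, with no record of that, is credited to the later dose.

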3. TOXICITY TABLES FOR USE IN TRIALS ENROLLING HEALTHY ADULTS

The abbreviations used in the following tables are:

ALT: alanine aminotransferase; aPTT: activated partial thromboplastin time; AST: aspartate aminotransferase; AV block: atrioventricular block; bpm: beats per minute; CK: creatine kinase; FEV₁: forced expiratory volume in 1 second; g: gram; HI: high; HPF: high power field; INR: international normalized ratio; IV: intravenous; LO: low; mEq: milliequivalent; mm Hg: millimeter of mercury; N: not graded; PT: prothrombin time; PTT: partial thromboplastin time; QTc: QT-interval corrected for heart rate; QTcB: Bazett's corrected QT interval; QTcF: Fridericia's corrected QT interval; RBC: red blood cell; Rx: therapy; ULN: upper limit of normal

CLINICAL ADVERSE EVENTS

Grading scale used for clinical adverse events is adapted from the Division of Microbiology and Infectious Diseases (DMID) Toxicity Tables (2014). For adverse events not included in the tables below, refer to the severity criteria guidelines in Section 12.1.3 of the CTP¹.

Cardiovascular	Grade 1	Grade 2	Grade 3
Arrhythmia		Asymptomatic, transient signs, no Rx required	Recurrent/persistent; symptomatic Rx required
Hemorrhage, blood loss	Estimated blood loss ≤100 mL	Estimated blood loss >100 mL, no transfusion required	Transfusion required
QTcF (Fridericia's correction) ^a or QTcB (Bazett's correction)	Asymptomatic, QTc interval 450-479 ms, OR Increase in interval <30 ms above baseline	Asymptomatic, QTc interval 480-499 ms, OR Increase in interval 30-60 ms above baseline ^b	Asymptomatic, QTc interval ≥500 ms, OR Increase in interval ≥60 ms above baseline
PR interval (prolonged)	PR interval 0.21-0.25 s	PR interval >0.25 s	Type II 2nd degree AV block OR Ventricular pause >3.0 s
Respiratory	Grade 1	Grade 2	Grade 3
Cough	Transient; no treatment	Persistent cough	Interferes with daily activities
Bronchospasm, acute	Transient; no treatment; FEV ₁ 71%-80% of peak flow	Requires treatment; normalizes with bronchodilator; FEV ₁ 60%-70% (of peak flow)	No normalization with bronchodilator; FEV ₁ <60% of peak flow
Dyspnea	Does not interfere with usual and social activities	Interferes with usual and social activities, no treatment	Prevents daily and usual social activity or requires treatment
Gastrointestinal	Grade 1	Grade 2	Grade 3
Nausea/vomiting	Minimal symptoms; caused minimal or no interference with work,	Notable symptoms; required modification in activity or use of	Incapacitating symptoms; required bed rest and/or resulted in loss of work or

^a Inclusion dependent upon protocol requirements.

^b The Grade 2 increase in interval is changed from 30-50 ms to 30-60 ms since the original DMID Toxicity Tables (2014) did not cover the increase in interval between 50 and 60 ms.

	school or self-care activities	medications; did not result in loss of work or cancellation of social activities	cancellation of social activities
Diarrhea	2-3 loose or watery stools or <400 g/24 hours	4-5 loose or watery stools or 400-800 g/24 hours	6 or more loose or watery stools or >800 g/24 hours or requires IV hydration
Reactogenicity	Grade 1	Grade 2	Grade 3
Local reactions			
Pain/tenderness at injection site	Aware of symptoms but easily tolerated; does not interfere with activity; discomfort only to touch	Notable symptoms; required modification in activity or use of medications; discomfort with movement	Incapacitating symptoms; inability to do work or usual activities; significant discomfort at rest
Erythema/redness ^a	2.5-5 cm	5.1-10 cm	>10 cm
Induration/swelling ^b	2.5-5 cm and does not interfere with activity	5.1-10 cm or interferes with activity	>10 cm or prevents daily activity
Itching at the injection site	Minimal symptoms; caused minimal or no interference with work, school or self-care activities	Notable symptoms; required modification in activity or use of medications; did not result in loss of work or cancellation of social activities	Incapacitating symptoms; required bed rest and/or resulted in loss of work or cancellation of social activities
Systemic reactions			
Allergic reaction	Pruritus without rash	Localized urticaria	Generalized urticaria; angioedema or anaphylaxis
Headache	Minimal symptoms; caused minimal or no interference with work, school or self-care activities	Notable symptoms; required modification in activity or use of medications; did not result in loss of work or cancellation of social activities	Incapacitating symptoms; required bed rest and/or resulted in loss of work or cancellation of social activities
Fatigue/malaise	Minimal symptoms; caused minimal or no interference with work, school or self-care activities	Notable symptoms; required modification in activity or use of medications; did not result in loss of work or cancellation of social activities	Incapacitating symptoms; required bed rest and/or resulted in loss of work or cancellation of social activities
Myalgia	Minimal symptoms; caused minimal or no interference with work, school or self-care activities	Notable symptoms; required modification in activity or use of medications; did not result in loss of work or cancellation of social activities	Incapacitating symptoms; required bed rest and/or resulted in loss of work or cancellation of social activities

^a In addition to grading the measured local reaction at the greatest single diameter, the measurement should be recorded as a continuous variable.

^b Induration/swelling should be evaluated and graded using the functional scale as well as the actual measurement.

Arthralgia	Minimal symptoms; caused minimal or no interference with work, school or self-care activities	Notable symptoms; required modification in activity or use of medications; did not result in loss of work or cancellation of social activities	Incapacitating symptoms; required bed rest and/or resulted in loss of work or cancellation of social activities
Reactogenicity	Grade 1	Grade 2	Grade 3
Chills	Minimal symptoms; caused minimal or no interference with work, school or self-care activities	Notable symptoms; required modification in activity or use of medications; did not result in loss of work or cancellation of social activities	Incapacitating symptoms; required bed rest and/or resulted in loss of work or cancellation of social activities

LABORATORY TOXICITY GRADING

Grading scale used for lab assessments is based on ‘FDA’s Toxicity Grading Scale for Healthy Adult and Adolescent Volunteers Enrolled in Preventive Vaccine Clinical Trials’, but grade 3 and 4 are pooled below, consistent with the 3 scale toxicity grading used throughout the protocol. If a laboratory value falls within the grading as specified below but also within the local laboratory normal limits, the value is considered as normal. For hemoglobin only the change from reference is used for the grading. The FDA table does not include toxicity grading for hematocrit, RBC counts or INR.

Blood, Serum, or Plasma Chemistries^a	LO/HI/N^b	Mild (Grade 1)	Moderate (Grade 2)	Severe (Grade 3)
Sodium (mEq/L or mmol/L)	LO	132-134	130-131	≤129
	HI	144-145	146-147	≥148
Potassium (mEq/L or mmol/L)	LO	3.5-3.6	3.3-3.4	≤3.2
	HI	5.1-5.2	5.3-5.4	≥5.5
Glucose (mg/dL)	LO	65-69	55-64	≤54
	HI ^c	100-110	111-125	>125
	HI ^d	110-125	126-200	>200
Blood urea nitrogen	HI	23-26 (mg/dL)	27-31 (mg/dL)	>31 (mg/dL)
Creatinine	HI	1.5-1.7 (mg/dL)	1.8-2.0 (mg/dL)	>2.0 (mg/dL)
Calcium (mg/dL)	LO	8.0-8.4	7.5-7.9	<7.5
	HI	10.5-11.0	11.1-11.5	>11.5
Magnesium (mg/dL)	LO	1.3-1.5	1.1-1.2	<1.1
Phosphorus (mg/dL)	LO	2.3-2.5	2.0-2.2	<2.0
CK (mg/dL)	N	1.25-1.5 x ULN	1.6-3.0 x ULN	≥3.1 x ULN
Albumin (g/dL)	LO	2.8-3.1	2.5-2.7	<2.5
Total protein (g/dL)	LO	5.5-6.0	5.0-5.4	<5.0
Alkaline phosphatase (U/L)	N	1.1-2 x ULN	2.1-3 x ULN	>3 x ULN
AST (U/L)	HI	1.1-2.5 x ULN	2.6-5 x ULN	>5 x ULN
ALT (U/L)	HI	1.1-2.5 x ULN	2.6-5 x ULN	>5 x ULN
Bilirubin, serum total (mg/dL) – when accompanied by any increase in Liver Function Test		1.1–1.25 x ULN	1.26–1.5 x ULN	>1.5 x ULN
Bilirubin, serum total (mg/dL) – when Liver Function Test is normal		1.1–1.5 x ULN	1.6–2.0 x ULN	>2.0 x ULN
Amylase (U/L)	N	1.1-1.5 x ULN	1.6-2.0 x ULN	>2.0 x ULN
Lipase (U/L)	N	1.1-1.5 x ULN	1.6-2.0 x ULN	>2.0 x ULN
Hematology	LO/HI/N^e	Mild (Grade 1)	Moderate (Grade 2)	Severe (Grade 3)
Hemoglobin (women) change from baseline (g/dL)	LO	Any decrease-1.5	1.6-2.0	>2.0
Hemoglobin (men) change from	LO	Any decrease-	1.6-2.0	>2.0

^a Depending upon the laboratory used, reference ranges, eligibility ranges and grading may be split out by sex and/or age.

^b Low, High, Not Graded.

^c Fasting.

^d Non-fasting.

^e Low, High, Not Graded.

baseline (g/dL)		1.5		
White blood cell count (cell/mm ³)	HI	10,800-15,000	15,001-20,000	>20,000
	LO	2,500-3,500	1,500-2,499	<1,500
Lymphocytes (cell/mm ³)	LO	750-1,000	500-749	< 500
Neutrophils (cell/mm ³)*	LO	1,500-2,000	1,000-1,499	< 1000
Eosinophils (cell/mm ³)	HI	650-1500	1501-5000	> 5000
Platelets (cell/mm ³)	LO	125,000-140,000	100,000-124,999	<100,000
Coagulation				
PT (seconds)	HI	1.0-1.10 x ULN	1.11-1.20 x ULN	>1.20 x ULN
International Normalized Ratio (INR) ^a	HI	1.1-1.5 x ULN	1.6-2.0 x ULN	>2.0 x ULN
PTT or aPTT (seconds)	HI	1.0-1.2 x ULN	1.21-1.4 x ULN	>1.4 x ULN
Fibrinogen (mg/dL)	HI	400-500	501-600	>600
	LO	150-200	125-149	<125
Urine				
Protein (dipstick)	HI	Trace	1+	2+
Glucose (dipstick)	HI	Trace	1+	2+
Blood (microscopic) - red blood cells per high power field (RBC/HPF)	HI	1-10	11-50	>50 and/or gross blood

* For African subjects, the following absolute neutrophil counts should be used to determine the severity level: grade 1 = 750 – 999 cell/uL; grade 2 = 500-749 cells/uL; grade 3 <500 cells/uL

^a For INR, the values in the table are based on the Division of AIDS Table for Grading the Severity of Adult and Pediatric Adverse Events, 2009.

RANGES TO CONVERT FDA SCALE (mg/dL) TO SI UNITS

Blood, Serum, or Plasma Chemistries^a	LO/HI/N^b	Mild (Grade 1)	Moderate (Grade 2)	Severe (Grade 3)
Glucose (mmol/L)	LO	3.61-3.38	3.05-3.60	≤3.04
	HI ^c	5.55-6.11	6.12-6.94	>6.94
	HI ^d	6.11-6.94	6.95-11.10	>11.10
Blood urea nitrogen (mmol/L)	HI	8.2-9.3	9.4-11.1	>11.1
Creatinine (μmol/L)	HI	133-150	151-177	>177
Calcium (mmol/L)	LO	2.00-2.10	1.87-1.99	<1.87
	HI	2.62-2.74	2.75-2.87	>2.87
Magnesium (mmol/L)	LO	0.53-0.62	0.45-0.52	<0.45
Phosphorus (mmol/L)	LO	0.74-0.81	0.65-0.73	<0.65
Cholesterol (mmol/L)	HI	5.20-5.43	5.44-5.82	>5.82
Coagulation				
Fibrinogen (μmol/L)	HI	11.76-14.70	14.71-17.65	>17.65
	LO	4.41-5.88	3.68-4.40	<3.68

VITAL SIGNS TOXICITY GRADING

Grading scale used for vital signs is according to DMID Toxicity Tables (2014)

Vital Signs	LO/HI/N^e	Mild (Grade 1)^f	Moderate (Grade 2)	Severe (Grade 3)
Fever (°C) ^g	HI	38.0-38.4	38.5-38.9	>38.9
Fever (°F)	HI	100.4-101.1	101.2-102.0	>102.0
Tachycardia	HI	101-115 bpm	116-130 bpm	>130 bpm or ventricular dysrhythmias
Bradycardia	LO	50-54 or 45-50 bpm if baseline <60 bpm	45-49 or 40-44 bpm if baseline <60 bpm	<45 or <40 bpm if baseline <60 bpm
Hypertension (systolic) - mm Hg ^h	HI	141-150	151-160	>160
Hypertension (diastolic) - mm Hg	HI	91-95	96-100	>100
Hypotension (systolic) - mm Hg	LO	85-89	80-84	<80
Tachypnea - breaths per minute	HI	23-25	26-30	>30

^a Depending upon the laboratory used, reference ranges, eligibility ranges and grading may be split out by sex and/or age.

^b Low, High, Not Graded.

^c Fasting.

^d Non-fasting.

^e Low, High, Not Graded.

^f If initial bound of grade 1 has gap from reference range or eligibility range, calculations based on the New England Journal of Medicine (NEJM) reference ranges.

^g Oral or axillary body temperature. A protocol should select either °C or °F for inclusion.

^h Assuming subject is awake, resting, and supine or sitting; for adverse events, 3 measurements on the same arm with concordant results.

